#### 5.7.3 UDS Test Results

See Section 6.8 for derivation of UDS test results.

Positive results of UDS at Screening, Induction Day 1 (of all induction attempts), Week 1 Day 1, and Weeks 2 through 6 (nominal visits) will be summarised for opiates/morphine, fentanyl, BUP (Screening Visit and first Induction Day 1 attempt only), methadone, and opioids (overall) for the SFAS overall and by induction arm, using observed data and descriptive statistics (number and percent of participants). Positive results for other non-opioid drug substances tested will be summarized in a similar manner.

The denominator for the summary of each UDS test will be the number of participants who have a non-missing result for that test.

#### 5.7.4 Demographic and Baseline Characteristics

Demographic and baseline characteristics (age, sex, race, ethnicity, childbearing potential, weight, height, body mass index, alcohol use, nicotine use, xanthine/caffeine use) and disease history (the randomisation strata, the UDS fentanyl result at the most recent Induction Day 1 Visit, medication for OUD, inclusion criterion 5a/5b met) at Screening will be summarised for the SFAS using descriptive statistics.

#### 5.7.6 Subgroup/Subpopulation analyses

The following analyses will be repeated for the fentanyl-positive and fentanyl-negative subpopulations, as defined by the eCRF same-day UDS result for fentanyl on the Induction Day 1 Visit of the most recent induction attempt.

- Primary endpoint (Section 5.3)
- Secondary endpoints (Section 5.4)

- AEs (Section 5.6.2)
- Concomitant medications (Section 5.5.2)
- COWS (Section 5.5.3)
- UDS results
- Participant disposition
- Demographic and baseline characteristics
- Exposure

Analyses of the primary endpoint (Section 5.3) will be repeated for the following subpopulations.

- •
- Participants who are randomised and inducted with neither RI or SoC (which is a key protocol deviation).

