4.1.2 Induction

When the participant has met the TM buprenorphine dosing criteria, he/she will be randomised at a 2:1 ratio to 1 of 2 induction arms: RBP-6000 rapid induction or SoC induction. Due to the potential for fentanyl use to impact the response to TM buprenorphine induction, randomisation will be stratified according to the same-day UDS result for fentanyl (negative or positive).

The following points apply to both induction arms:

- After randomisation, the participant will complete the pre-TM buprenorphine assessments: vital signs, 12-lead electrocardiogram (ECG) and a review of AEs.
- If the participant displays any allergic/hypersensitivity reaction to TM buprenorphine, the participant will be discontinued from the study.
- Participants experiencing precipitated withdrawal symptoms post-TM buprenorphine may be treated symptomatically (see Section 9.13).

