4.1.2.1 Rapid Induction

The flow of activities for participants in the rapid induction arm is provided in Figure 3.

After completing the pre-TM buprenorphine assessments, participants will then be administered 4 mg of TM buprenorphine.

After a minimum of 1 hour has elapsed since the 4-mg dose of TM buprenorphine was administered, the participant will be re-assessed for withdrawal symptoms (COWS) and tolerability (AEs). Participants must meet **all** of the following criteria to receive RBP-6000 using rapid induction:

- 1. The participant does not display any allergic/hypersensitivity reaction to TM buprenorphine.
- 2. Based on the Investigator's judgment, the participant did not experience precipitated withdrawal symptoms from the most recent TM buprenorphine administration that would prevent RBP-6000 administration.
- 3. Based on the Investigator's judgment, the participant is not sedated (i.e., participant cannot be easily aroused by external stimuli).

After receiving TM buprenorphine, if the participant is sedated or has precipitated withdrawal symptoms that would prevent RBP-6000 administration, in the opinion of the Investigator, the participant may either remain in the clinic to repeat the 4 mg TM buprenorphine later that same day or may return to the site and repeat the induction within 30 days of informed consent.

If the participant is eligible for dosing with RBP-6000, pre–RBP-6000 assessments will be conducted including, but not limited to, vital signs, will be collected. If the participant is eligible, 300 mg RBP-6000 may be administered SC and the visit will be considered Day 1.

Participants will be asked to remain in the clinic for at least 4 hours post-RBP-6000. A COWS assessment will be completed at 1, 2 and 4 hours and an injection site evaluation will be completed at 1 and 2 hours post–RBP-6000.

[figure not shown]
All AEs and concomitant medications should be recorded. If the participant experiences withdrawal symptoms post RBP-6000 on Day 1, the participant may be treated symptomatically (SAMHSA TIP 63 2020; see Section 9.13 for treatment of withdrawal symptoms). Also, following the first injection of 300 mg RBP 6000, TM buprenorphine in increments of 2 to 4 mg up to a maximum dose of 12 mg (inclusive of pre–RBP-6000 TM buprenorphine) may be administered on Day 1 at the discretion of the Investigator to alleviate withdrawal symptoms while on site.

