5.9 Participant Rescreening

Participants not meeting one or more inclusion/ exclusion criteria will be screen failures. Participants who have a change in clinical status may be rescreened with documented approval of the Sponsor's Medical Monitor.

Eligible participants who were not randomized to an induction arm (Section 4.1.2) within the 30-day screening period, may be rescreened for study participation following documented approval of the Medical Monitor.

Eligible participants who were randomized to an induction arm (Section 4.1.2), may not be rescreened, regardless of whether they were administered TM buprenorphine.

If a participant is rescreened, all screening assessments, as described in Appendix 22.1, will be repeated, including the re-signing of informed consent. The 30-day screening window will begin upon signature of the informed consent.

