9.13 Permitted Concomitant Therapies

The Investigator may prescribe concomitant medications or treatments deemed necessary to the participant, except those medications defined in Section 9.10 and Section 9.11 of this protocol.

If the participant experiences withdrawal symptoms at any time (including withdrawal after RBP-6000), he/she may be treated symptomatically (SAMHSA TIP 63 2020):

- Nausea: ondansetron or metoclopramide
- Diarrhoea: loperamide
- Anxiety, irritability, sweating: clonidine
- Insomnia: diphenhydramine, trazodone
- Pain: nonsteroidal anti-inflammatory drugs

Participants who experience opioid withdrawal after RBP-6000 administration may be treated with non-opioid medications as described above.

For rapid induction participants, if precipitated withdrawal occurs post TM buprenorphine that would prevent RBP-6000 administration, an additional 4 mg TM buprenorphine may be re-administered later that same day at the discretion of the Investigator. Alternatively, the Investigator may permit the participant to return to the

facility on another day within 30 days of informed consent. Returning participants will repeat all Day 1 scheduled assessments. In addition for rapid induction participants, adjunctive use of TM buprenorphine in increments of 2 to 4 mg up to a maximum of 12 mg may be administered on Day 1 (i.e., 12 mg total TM buprenorphine on Day 1, inclusive of pre–RBP-6000 TM buprenorphine) at the discretion of the Investigator to alleviate withdrawal symptoms after the first injection of RBP-6000.

Investigators will be asked to identify concomitant medications administered to alleviate withdrawal symptoms.

Participants will not be discontinued from treatment due to non-prescribed opioid use (including TM buprenorphine), but use should be captured on the TLFB.

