#### 5.1.5 Randomisation Stratification Variable

The OLIS randomisation is stratified according to the same-day UDS result for fentanyl (negative or positive) on the first induction attempt. The same-day UDS result for fentanyl will be recorded in the eCRF, and the randomisation system will utilise the value recorded at the time of randomisation to assign the randomisation stratum. There is a possibility the incorrect stratum is used for randomisation, in the event the same-day UDS result for fentanyl recorded in the eCRF on the first induction attempt is corrected following randomisation. However, the stratum used for randomisation will be used for analyses involving stratum. See Section 5.7.6 for analyses by fentanyl-positive and fentanyl-negative UDS subpopulations, as defined by the eCRF same-day UDS result for fentanyl on the Induction Day 1 Visit of the most recent induction attempt.

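### The fentanyl subpopulations in SAP 5.7.6 use the most recent induction attempt, which for participants who repeat induction after randomisation is a post-randomisation value

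*SAP*

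**What the plan says.** SAP 5.7.6 repeats the primary and secondary endpoints, adverse events, concomitant medications, COWS, UDS results, disposition, baseline characteristics and exposure in two fentanyl subpopulations, "as defined by the eCRF same-day UDS result for fentanyl on the Induction Day 1 Visit of the most recent induction attempt". SAP 5.1.5 points to the same definition.

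The randomisation stratum is a different variable. SAP 5.1.5 states: "The OLIS randomisation is stratified according to the same-day UDS result for fentanyl (negative or positive) on the first induction attempt". It adds that "the stratum used for randomisation will be used for analyses involving stratum", even if the eCRF value is corrected later.

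On timing, Protocol 4.1.2 states: "When the participant has met the TM buprenorphine dosing criteria, he/she will be randomised at a 2:1 ratio". Pre-dose assessments and the first TM buprenorphine dose follow.

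On repeats, Protocol 4.1.2.1 says that an RI participant who is sedated, or has precipitated withdrawal that prevents the injection, can be re-dosed that day or "may return to the site and repeat the induction within 30 days of informed consent". Protocol 9.7.1 and 9.13 say much the same, and 9.13 adds: "Returning participants will repeat all Day 1 scheduled assessments". The schedule in Protocol 22.2 places a UDS at check-in on the first or repeat induction day. Protocol 5.9 rules out a fresh start: "Eligible participants who were randomized to an induction arm (Section 4.1.2), may not be rescreened".

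**The concern.** A subgroup comparison keeps the protection of randomisation when membership is fixed before allocation. Here the membership of some participants is fixed afterwards, by a test taken because the first attempt did not lead to an injection. The same person could fall in different fentanyl subgroups depending on the arm assigned, because the chance of a repeat can depend on the arm.

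Fentanyl status was made the stratification factor because fentanyl may affect the response to TM buprenorphine (Protocol 4.1.2), so these subgroup tables are likely to be read closely. Two things are at stake: the RI–SoC retention contrast within each subpopulation, and the subgroup to which early adverse events are attributed.

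**Working it through.** **1. Whose classification can change**

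| Participant | Value used in SAP 5.7.6 | Affected? |
|---|---|---|
| One attempt | Pre-randomisation result | No |
| Rescheduled before randomisation (COWS below 8, or recent long-acting opioid; Protocol 4.1.1) | Still pre-randomisation if no later repeat | No |
| Repeats after randomisation and dosing, same fentanyl result | Post-randomisation, same subgroup | No |
| Repeats after randomisation and dosing, different result | Post-randomisation, other subgroup | Yes |

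Only the last row matters. The documents give neither its size nor its split by arm.

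**2. The plan's own design figure**

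SAP section 3 gives 77.2% power at 70% retention in both arms. A simulation used 100,000 trials per scenario, Beta(1,1) priors, looks at 80/40, 160/80 and 326/163 participants, and success at a posterior probability of at least 96%. Cumulative power was 29.1%, 52.0% and 77.4%, against 29.4%, 51.7% and 77.2% in the SAP. Overall type I error was 0.092 to 0.098, against 0.0916 to 0.0978. The design figures reproduce. They concern the unstratified overall comparison (SAP 5.3.2), which does not use the fentanyl subgroup.

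**3. Illustration of the subgroup bias**

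Inputs from the documents: 489 participants randomised 2:1, so N = 326 in RI; planning retention of 70%; margin of 10 points. Everything else is assumed:

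- p: share fentanyl-positive at randomisation
- r: share of RI participants who repeat
- c: share of positive repeaters who return negative
- d: how many points worse those who change are retained
- 70% retention in both arms and both baseline strata, no repeats in SoC, and no negative-to-positive changes

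The number who change is m = N × p × r × c. The false RI–SoC differences are:

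- fentanyl-negative: −m × d / [N(1 − p) + m]
- fentanyl-positive: +m × d / [Np − m]

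Case A (p = 70%, r = 10%, c = 30%, d = 20):

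- m = 326 × 0.70 × 0.10 × 0.30 = 6.8
- negative: −6.8 × 20 / (97.8 + 6.8) = −1.3 points
- positive: +6.8 × 20 / (228.2 − 6.8) = +0.6 points

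Case B (p = 70%, r = 10%, c = 25%, d = 30):

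- m = 326 × 0.70 × 0.10 × 0.25 = 5.7
- negative: −5.7 × 30 / (97.8 + 5.7) = −1.7 points
- positive: +5.7 × 30 / (228.2 − 5.7) = +0.8 points

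Range with d = 30, p from 50% to 80%, r from 5% to 20% and c from 10% to 50%:

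- smallest: m/N = 0.50 × 0.05 × 0.10 = 0.0025, giving −0.0025 × 30 / 0.5025 = −0.15 (negative) and +0.0025 × 30 / 0.4975 = +0.15 (positive)
- largest: m/N = 0.80 × 0.20 × 0.50 = 0.08, giving −0.08 × 30 / 0.28 = −8.6 (negative) and +0.08 × 30 / 0.72 = +3.3 (positive)

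The bias is zero if d = 0, if no result changes, or if SoC repeats and changes in the same way. If those who change are retained better than the rest, both signs reverse. With a pre-randomisation fentanyl value, the false difference is zero by construction in every scenario.

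**4. Adverse events**

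SAP 5.4.2.1 counts adverse events from the first TM buprenorphine dose across all induction attempts. SAP 5.7.6 assigns the participant by the last attempt. Suppose an RI participant is fentanyl-positive, has precipitated withdrawal, returns on another day and tests negative. The first-attempt event is then tabulated as fentanyl-negative. This follows from the two definitions and needs no assumed rate.

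**The case against.** The best defence is that the choice is deliberate and open. SAP 5.1.5 separates the stratum from the subpopulation. The most recent attempt is also the one used for time to discontinuation (5.4.1.1), COWS (5.5.3) and parts of exposure (5.6.1), and fentanyl status at the induction being analysed is a coherent clinical descriptor. SAP 5.7.2, 5.7.3 and 5.7.4 report multiple attempts, UDS at every attempt, and both fentanyl variables. No success criterion is attached to the subgroups. All of this stands. It supports keeping the most-recent version as a description, but it does not make that version a sound basis for comparing arms.

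A reader might infer more than the text supports:

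- **That every later attempt is after randomisation.** Reschedules for COWS below 8 or recent long-acting opioid use come before it.
- **That only RI participants repeat.** The explicit rule for returning after TM buprenorphine is written for RI, while SoC participants return for dose adjustment (Protocol 4.1.2.2). But SAP 5.1.4 lists reasons for repeats without limiting them to an arm, and 5.6.1 summarises attempts in both arms. Same-day re-dosing also means that not every failed first dose leads to a return visit.
- **That results by a pre-randomisation fentanyl value are missing altogether.** Injection receipt (5.2.2), time to discontinuation (5.4.1.2), adverse events (5.4.2.2) and COWS (5.5.3) are also shown within randomisation strata. No Bayesian primary comparison by such a value is visible in the readable text, but one bullet in 5.7.6 is blank, so its absence cannot be stated flatly.
- **That status will readily turn from positive to negative.** Protocol 4.1.1 notes slow clearance of fentanyl, and the repeat must fall within 30 days of consent.

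**Conclusion.** The point holds in limited form. For participants who repeat induction after randomisation and dosing, SAP 5.7.6 uses a subgroup value that can depend on the response to treatment. The RI–SoC contrasts in the fentanyl subpopulations are therefore not fully protected by randomisation, and adverse events can be attributed to the wrong fentanyl group.

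The size cannot be derived from the documents. Under the two central sets of assumptions the false difference is about 1 to 2 points in the fentanyl-negative subgroup and under 1 point in the positive one. The wider range rests wholly on assumed rates and on changers being retained 30 points worse. Direction is uncertain: people who return for a second attempt are selected, and changes from negative to positive are also possible.

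It would be wrong to conclude that the sub-study's non-inferiority result is compromised. That decision uses the overall comparison, which this definition does not touch.

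**What to change.** For the arm comparisons in SAP 5.7.6 (primary and secondary endpoints, adverse events and disposition), define the subpopulations by the eCRF same-day fentanyl UDS, as corrected, from the induction day on which the participant was randomised. Naming that day avoids ambiguity for participants rescheduled before randomisation. Using the corrected value also deals with the mis-stratification problem raised in SAP 5.1.5 without bringing in a post-randomisation variable.

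Keep the most-recent-attempt version as a descriptive or sensitivity analysis; it suits the COWS summaries, which follow that attempt. Add a table by arm of how many participants change fentanyl status between the randomisation day and the most recent attempt. If that number is near zero, the two versions will agree and the question closes.

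The cost is a change of wording and one extra set of tables. No new data are needed, since UDS results from all induction attempts are already to be summarised (SAP 5.7.3). Sample size, power and the non-inferiority criterion do not change.

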#### 5.8 Interim Analyses

Two interim analyses of the primary endpoint (treatment retention at Injection 2) will be performed when all of the first 120/240 (at a minimum) participants who received TM BUP have either (1) received Injection 3, or (2) discontinued prior to Injection 3 (ie, they have completed the early termination visit or they have been discontinued per the eCRF disposition page). The interim analyses will be performed to allow early declaration of noninferiority of RI to SoC induction with respect to treatment retention at Injection 2. At each IA, the criterion of NI is the posterior probability of retention rate difference (RI – SoC) > -10% being 96% or greater. See Section 2.1 and Table 3 for information on the 1-sided Type I error at each IA, final analysis and overall.

Indivior study team personnel will perform the IA(s).

If NI is declared at the first or second IA, then the results will be shared within Indivior:

- A decision will be made whether to submit the results of the IA to regulatory authorities.
- If the results of the IA will be submitted to regulatory authorities, then all of the endpoints (primary, secondary,
   BUP plasma concentrations, participant disposition, and baseline demographics and disease history will be analysed for inclusion in the interim CSR.

If NI is declared at the first IA, then the second IA might not be performed.

If NI is not declared at the first or second IA, then there will not be any additional secondary analyses performed until the final analysis.

The analysis population for the IA is the Evaluable Population for Treatment Retention/Discontinuation, applied to the first 120/240 (at a minimum) participants defined above. Similarly, if analyses for an interim CSR will be performed, the analysis populations will be those noted for the final analysis, applied to the first 120/240 (at a minimum) participants defined above.

At an IA, the value of treatment retention at Injection 2 for each participant is assigned as Yes/No as described in Table 7.

Table 7. Interim Analysis: Assignment of Treatment Retention at Injection 2

Participant status	Treatment Retention at Injection 2
Received Injection 2 at Week 2 (nominal) Visit	Yes
Missed Injection 2 at Week 2 (nominal) Visit but received Injection 3 at Week 6 Day 36 Visit	Yes
Did not receive Injection 2 and discontinued prior to receiving Injection 3 (ie, they have completed the early termination visit or they have been discontinued per the eCRF disposition page and have no RBP-6000 administration data indicating receipt of Injection 2 or 3)	No
Missed Injection 2 at Week 2 (nominal) Visit, have not received Injection 3 at Week 6 Day 36 Visit, and the study disposition status has not been captured in the eCRF	No (imputed)

#### 6 SUPPORTING DOCUMENTATION

#### 6.1 Appendix 1: List of Abbreviations

Table 8. List of Abbreviations

Abbreviation	Term
AE	adverse event
ALQ	above the limit of quantitation
ALT	alanine aminotransferase
AST	aspartate aminotransferase

**Table 8. List of Abbreviations** 

Abbreviation	Term
ATC	Anatomic Therapeutic Chemical
BUP	buprenorphine
CI	confidence interval
COWS	Clinical Opiate Withdrawal Scale
eCRF	electronic case report form
FA	final analysis
IA	interim analysis
IES	intercurrent event strategy
IWRS	Interactive Web Response System
KM	Kaplan-Meier
LFT	liver function tests
MedDRA	Medical Dictionary for Regulatory Activities
NI	non-inferiority
OLIS	Open-label Induction Sub-study
OUD	opioid use disorder
PLS	population level summary
PT	preferred term
QTcF	QT interval corrected using Fridericia's method
RI	Rapid Induction
SAE	serious adverse event
SAP	statistical analysis plan
SD	standard deviation
SRP	Sub-study Randomised Population
SFAS	Sub-study Full Analysis Set
SoC	standard of care
SOC	System Organ Class
TEAE	treatment-emergent adverse event
TLFB	TimeLine Follow Back
TLF	tables, listings, and figures
TM	transmucosal
UDS	urine drug screen
ULN	upper limit of normal

## 6.2 Appendix 2: Changes to Protocol-Planned Analyses

The following are changes to the protocol-planned analyses:

• The Sub-study enrolled population (SEP) was renamed as the Sub-study Randomised Population (SRP), as this name better describes the population.

- - Some analyses using the SFAS will be repeated whereby the participants will be analysed corresponding to the treatment to which they were randomized ("as randomised", ie, planned arm).
  - An exploratory analysis approach for the Secondary Endpoint 1, Time to Treatment Discontinuation was added.
  - Only the UDS results will be summarised. The results from the TimeLine Follow Back (TLFB), alone and combined with the UDS were specified in the protocol but are not necessary to meet the objectives of the sub-study. These analyses will be performed for the main study.

- A categorical summary of change in COWS scores was added.
- For exposure analyses, a summary of the time elapsed between TM BUP and Injection 1 for the RI group was added.
- Analyses of vital signs, ECGs and LFTs were added.

#### 6.3 Appendix 3: Schedules of Events

The Schedules of Events can be found in the protocol.

#### 6.4 Appendix 4: Methods to Manage Missing Data

Observed data are used for analysis, unless handling of missing data is described otherwise within the analysis description or in the sections below.

#### 6.4.1 Missing Date Information for Adverse Events

If the AE start date is missing, and the AE stop date is on or after the first dose of study medication, then the AE start date will be imputed as the date of the first dose of study medication.

If the AE start date is missing, and the AE stop date is not missing and before the first dose of study medication, then the AE start date will be imputed as the stop date.

